11.4 Shipping Instructions

All samples are to be identified with the patie	nt's assigned re	egistration nu	mber and	shipped
with reference to Breast study	. Slides and T			
overnight express to the				
(BRS).				

Phase I/II Trial of Letrozole and Sorafenib as First-Line Therapy in Postmenopausal Women with Hormone Receptor-Positive Locally Advanced or Metastatic Breast Cancer PI:

Paraffin Blocks

Please wrap paraffin blocks in bubble wrap or some material that will cushion them. During spring and summer months paraffin blocks must be shipped with a cooler pack inside the shipping container or the wax will melt and the specimen will be compromised.

Glass Slides

Glass slides must be mailed/shipped in appropriate protective slide containers. These can be made of cardboard (flat slide holder) or plastic (slide box or slide shipper).

Documentation

Please have the name, address and the appropriate laboratory or office phone number of the institution that the patient specimens were shipped from. For any questions relating to shipment of samples please call

12. Pharmaceutical Information

12.1 Sorafenib

Name: Sorafenib. Sorafenib tosylate

is the tosylate salt of sorafenib

is the tosylate salt of sorafenib

[4-[3-(4-chloro-3-trifluoromethyl-phenyl) ureido]-phenoxy}-pyridine-2 carboxylic acid methylamide-4
methylbenzensulfonate and its molecular formula is

C₁₂H₁₆CIF₃N₄O₃XC₇H₈O₃S. Molecular weight of sorafenib (free base) is

465 Daltons and sorafenib tosylate is 637 Daltons.

How Supplied: BAY 43-9006 sorafenib 200 mg is supplied as round, biconvex, redfilm-coated tablets, debossed with the 'Bayer cross' on one side and '200' on the other side. The tablets contain BAY 43-9006 tosylate equivalent to 200 mg of the free base BAY 43-9006, and the excipients croscarmellose sodium, microcrystalline cellulose, hypromellose, sodium lauryl sulfate, and magnesium stearate. The film-coat consists of hypromellose, polyethylene glycol, titanium dioxide and red iron oxide. The film coating has no effect on the rate of release of the active BAY 43-9006 tosylate.⁴⁶

Sorafenib will not be provided and is commercially available. Patients will be given assistance on how to obtain sorafenib. Patients may have to pay for it or be responsible for any co-pays associated with obtaining drug supply.

Phase I/II Trial of Letrozole and Sorafenib as First-Line Therapy in Postmenopausal Women with Hormone Receptor-Positive Locally Advanced or Metastatic Breast Cancer PI:

Storage requirements/ Stability: Tablets are stable at room temperature. Do not store above 25°C (77°F). Store in the original package.. The current shelf life is 36 months.

Route of administration: The dose of sorafenib to be taken by patients will be determined from the phase I component of the trial. Sorafenib is available in immediate-release preparations and thus the active ingredient is completely dissolved in a short period of time after oral administration of film-coated tablets. Sorafenib should be taken on an empty stomach, at least 1 hour before or 2 hours after a meal. Tablets should be swallowed whole, not crushed or chewed, with 8 ounces or 250 ml of water. It should not be taken with grapefruit juice. 46

Expected toxicities: Adverse Drug Reactions in patients in multiple clinical trials

(MedDRA coded)

System Organ Class	Very Common > 10%	Common ≥ 1% to < 10%	Uncommon ≥ 0.1% to < 1%
Infections and infestations	_		Folliculitis infection
Blood and lymphatic system disorders	Lymphopenia	Leucopenia Neutropenia Anemia Thrombocytopenia	
Immune system disorders			Hypersensitivity reactions (including skin reactions and urticaria)
Endocrine disorders			Hypothyroidism
Metabolism and nutrition disorders	Hypophosphatemia	Anorexia	Hyponatremia Dehydration
Psychiatric disorders		Depression	
Nervous system		Peripheral sensory	Reversible posterior
disorders		neuropathy	leukoencephalopathy*
Ear and labyrinth disorders		Tinnitus	
Cardiac disorders			Myocardial ischemia and infarction* Congestive heart failure*
Vascular disorders	Hemorrhage (including gastrointestinal* and respiratory tract* and cerebral hemorrhage*) Hypertension		Hypertensive crisis*
Respiratory, thoracic and mediastinal disorders		Hoarseness	Rhinorrhea
Gastrointestinal	Diarrhea	Constipation	Gastro esophageal
disorders	Nausea	Stomatis (including dry	reflux disease

System Organ Class	Very Common ≥ 10%	Common ≥ 1% to < 10%	Uncommon ≥ 0.1% to < 1%
	Vomiting	mouth and glossodynea) Dyspepsia Dysphagia	Pancreatitis Gastritis Gastrointestinal perforation*
Hepato-biliary disorders			Increase in bilirubin and jaundice
Skin and subcutaneous tissue disorders	Rash Alopecia Hand-foot reaction** Pruritis Erythema	Dry skin Dermatitis exfoliative Acne Skin desquamation	Eczema Erythema multiforme minor
Musculoskeletal, connective tissue and bone disorders		Arthralgia Myalgia	
Reproductive system and breast disorders		Erectile dysfunction	Gynaecomastia
General disorders and administration site conditions	Fatigue Pain (inc. mouth, abdominal, bone pain, headache and tumor pain)	Asthenia Fever Influenza-like illness	
Investigations	Increased amylase Increased lipase	Weight decreased Transient increase in transaminases	Transient increase in blood alkaline phosphatase INR abnormal, prothrombin level abnormal

^{*} Events may have a life-threatening or fatal outcome. Such events are uncommon.

In combination with cytotoxic agents, myelosuppression leading to febrile neutropenia has also been observed. Such events may have a life-threatening or fatal outcome.

Drug Interactions: Based on numerous Phase I oxidative and Phase II glucuronidation metabolic pathway in vitro trials, the potential of sorafenib to interact with other drugs is low. The sorafenib tosylate is metabolized by the CYP P450 enzymatic pathway (specifically CYP3A) and therefore may interact with other drugs that utilize this pathway. Close monitoring is suggested in patients taking medications such as warfarin, carbamazepine, phenytoin, quinidine, phenobarbital, and digoxin, which are metabolized by the liver and have small therapeutic ranges. Sorafenib has been seen to increase levels of doxorubicin, docetaxel, and irinotecan, but the clinical importance of these elevations is unclear and currently being studied.

^{**} Palmar plantar erythrodysaethesia syndrome in MedDRA

Phase I/II Trial of Letrozole and Sorafenib as First-Line Therapy in Postmenopausal Women with Hormone Receptor-Positive Locally Advanced or Metastatic Breast Cancer PI:

12.2 Letrozole

How supplied: Letrozole will be supplied to patients at no cost by

It will be supplied as 2.5 mg tablets and one bottle will contain 30 tablets. Letrozole is available as a 2.5 mg dark yellow film-coated tablet. It is a synthetic achiral benzhydroltriazole derivative of the chemical name 4,4'[(1H-1,2,4-triazol-1-yl)methylene]bisbenzonitrile (MW 285.31). The compound formula C₁₇H₁₁N₅ is odorless, white to yellowish crystalline material, freely soluble in dichloromethane, slightly soluble in ethanol, and practically insoluble in water.

Storage and stability: Very stable at room temperature; shelf life is 2 years.

Route of administration: Patients will take one 2.5 mg tablet by mouth once a day. Letrozole is rapidly absorbed and completely bioavailable after oral administration of film-coated tablets.

Toxicities: The most frequently reported adverse events were headache, nausea, vomiting, peripheral edema, hot flashes, fatigue, hair thinning, bone pain, back pain, arthralgia, and dyspnea.

Drug interactions: Based on two pharmacokinetic drug interaction studies (warfarin, cimetidine), review of data from large Phase III trials, and the in vitro results on cytochrome P450 enzymes, the potential of letrozole to interact with other drugs is low. No dose adjustments are recommended nor required for patients with renal or liver impairment.

12.3 Drug Accountability

The investigator is required to maintain adequate records of receipt, dispensing and final disposition of study drug. This responsibility has been delegated to the pharmacy. Include on receipt record (e.g. packing slip) from and to whom study drug was shipped, date, quantity, and batch or lot number. On dispensing record, note quantities and dates study drug was dispensed to and returned by each subject.

12.4 Drug Destruction/Disposal

Empty and partially empty containers of study drug will be disposed of in accordance with institutional policies and procedures. Unused containers of study drug will be returned to the study sponsor following completion of the study.

13. Data Collection and Records to be Kept

13.1 Electronic Case Report Forms

The Plat each institution will be responsible for assuring that all data specified in the study-specific data capture plan is collected and entered onto the electronic case report forms (eCRFs).

Phase I/II Trial of Letrozole and Sorafenib as First-Line Therapy in Postmenopausal Women with Hormone Receptor-Positive Locally Advanced or Metastatic Breast Cancer PI:
Data submission guidelines are in concordance with those expected by the National Cancer Institute, i.e.: Baseline data is to be entered onto eCRFs within 2 weeks of initiation of treatment. Subsequent eCRFs are to be completed within 2 weeks of the date in which the previous cycle was completed. All e-CRFs will be submitted to the OHRS at the via its secure web-based data management system. The e-CRFs are found in the study specific calendar that has been created in the data management system. The system will prompt the user to the forms that are required based upon the patient's enrollment and treatment dates.
Periodically, monitoring and/or auditing visits will be conducted by the monitoring/auditing staff for the purpose of verifying data entered onto eCRFs with source documentation. The participating institution will provide access to the patient's original records to permit verification data entry.
13.2 Research Charts A research chart (i.e., shadow chart) is maintained at OHRS for each patient enrolled. Copies of the most significant study source documents will be maintained in the research chart. Examples of source document copies that will be maintained in the research chart include: signed informed consent form, documents that verify eligibility and treatment and documents that verify Grade 3-4 adverse events and response. This information will be updated on a prospective basis and will be confidentially maintained at the OHRS.
Publications and annual reports for submission to the IRB and FDA will be written by the PI using the data captured on the CRFs. Study progress reports will be provided to participating institutions for submission to local IRBs.
Monitoring of this study will occur in accordance with the NCI approved Data and Safety Monitoring Plan (DSMP). An "initiation audit" will be conducted by OHRS Quality Assurance staff in accordance with the DSMP following enrollment of the first two (2) or three (3) patients. Subsequent audits will occur on an annual basis if the findings from the initiation audit were satisfactory. More frequent audits of patient data and study conduct will occur if necessary. All

15. Multi-Institutional Guidelines

15.1 IRB Approvals

As the Coordinating Center for a trial, it is the coordinating center's responsibility to ensure that no patients are entered on the trial at a participating institution without full IRB approval. Thus, OHRS will approve the addition of each participating institution to the

quarterly and audited annually. Prior audit findings and/or situations that may arise during the course of the study will determine the need for more frequent auditing. All audit findings will

be reported to the PI, Human Research Oversight Committee (HROC) and to the Institutional Review Board.

Phase I/II Trial of Letrozole	and Sorafenib	as First-Line Therapy in Postmenopausal
Women with Hormone Receptor-P	ositive Locally Advanced	
PI:	•	

study. A copy of the IRB approval document from each participating institution will be obtained prior to activation of the study at the participating institution.

15.2 Other Pre-Study Documents

Each participating center is required to have the following documents on file at the OHRS:

- Curricula Vitae of all physician Investigators
- Signed FDA form 1572 of all physician Investigators
- Rutgers Financial Disclosure of all physician Investigators if site is under the Rutgers IRB of record. If a site utilizes their local IRB, their approval covers this and would not applyDocumentation of Human Subjects Protection training from all Investigators
- Medical license from each Investigator

15.3 Initiation Site Visit/Meeting

A study initiation meeting will be conducted with each participating institution prior to enrollment of patients from the institution. OHRS staff will conduct the study initiation meeting in close proximity to IRB approval of the study at the participating center. In most situations the study initiation meeting will be conducted via teleconference.

15.4 IRB Continuing Approvals

Investigators from participating institutions must provide a copy of the institution's approved continuing review documentation. Registration will be halted at any participating institution in which a current continuing approval is not on file at OHRS. Centers who are approved to utilize the Board will not be required to file continuing review documentation.

15.5 Amendments and Consents

15.6 Patient Registration

All patients from participating institutions must register patients with the OHRS central registration desk, as described in Section 5.7 of this protocol.

15.7 Data Collection and Toxicity Reporting

The PI at each institution will be responsible for assuring that all the required data is collected and entered onto the eCRFs accurately and completed eCRFs submitted as described in Section 13.

Phase I/II Trial of Letrozole and Sorafer	as First-Line Therapy in Postmenopausa
Women with Hormone Receptor-Positive Locally	Advanced or Metastatic Breast Cancer
PI:	
15.8 Data Monitoring and Source Do	ocument Verification

Each site participating in the accrual of patients to this protocol will be audited for protocol and regulatory compliance, data verification and source documentation.

The staff will conduct remote monitoring on a continual basis of participating institutions with monitoring visits occurring as necessary. The monitoring visits will focus on verifying data with source documents. Adherence to the protocol(s), including the prompt reporting of serious adverse events, will be assessed. Findings of all monitoring visits are recorded on a Monitors Report, which is kept in the OHRS regulatory file. Issues concerning study compliance are reviewed at regular meetings with the HROC.

15.9 Data and Center Audits

staff will conduct annual audits to participating centers in accordance with OHRS Standard Operating Procedures (SOPs). The audit guidelines are in accordance with the and Safety Monitoring Plan.

16. Statistical Considerations

16.1 Primary and Secondary Hypotheses

The study will require a short run-in phase I portion to determine the recommended phase II dose. The primary objective of the single arm single-stage phase II portion of the study is to determine the clinical benefit rate (proportion of patients who achieve a complete response, partial response, or stable disease ≥ 6 months) of letrozole and sorafenib as first-line therapy in postmenopausal women with hormone receptor-positive locally advanced or metastatic breast cancer. The secondary objectives are to determine the safety and tolerability of sorafenib in combination with letrozole and evaluate time to progression and overall survival.

16.2 Sample Size Justification

A historical study showed that single-agent letrozole in the first-line treatment of patients with hormone receptor-positive metastatic breast cancer had a clinical benefit rate of 50% compared to tamoxifen. The combination therapy of letrozole and sorafenib will not be considered of further interest if the true clinical benefit rate is less than or equal to 50%. We assume that this study will target a clinical benefit rate of 67% for identifying the combination therapy as active and worthy of further investigation. With these settings, the null hypothesis is that the clinical benefit rate of the combination therapy is less than or equal to 50%, and the alternative hypothesis is that the clinical benefit rate of 67% or more is of considerable interest. For the phase II part of the study, the sample size was calculated according to a single-stage design. The study will accrue a total of 58 patients, and the combination therapy will be accepted if there are at least 35 responders out of 58 patients. The design will have a 4.3% (< 5%) type-I error (false positive) rate and a power of 82.7% (> 80%) (i.e., 17.3% type-II error or false negative rate). The total number of evaluable patients to be accrued to this study is not expected to exceed 64 patients.

Phase I/II Trial of Letrozole (and Sorafenib as First-Line Therapy in Postmenopausal Women with Hormone Receptor-Positive Locally Advanced or Metastatic Breast Cancer PI:

The patients accrued in the Phase I dose escalation will be included in the Phase II portion if they receive the same dose. Evaluable patients for the phase I portion are defined as study-eligible patients who have received at least one cycle of treatment. Evaluable patients for the phase II portion are those who have received at least two cycles of treatment.

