2.1 Introduction

In 2007, over 178,480 women will be diagnosed with invasive breast cancer and 40,460 women will die of this disease. Although the last two decades have witnessed significant advances in systemic therapies, metastatic breast cancer still remains an incurable disease. Once metastases are discovered, median survival for all patients is only two to three years. Given the lack of curable treatment, the major goals of therapy include palliation of symptoms, maintenance of quality of life, and improvement in overall and progression-free survival. When choosing the optimal therapy for metastatic breast cancer, one must take into account a number of factors, such as the likelihood of response with a particular therapy, its side effect profile, and ease of administration. In addition, consideration of an individual tumor's biology allows the tailoring of therapy to optimize resources and outcomes.

Hormonal therapy, such as selective estrogen receptor modulators, aromatase inhibitors, and estrogen antagonists, is a major treatment option for women with hormone receptor-positive metastatic breast cancer. Approximately 75% of breast cancers are positive for the estrogen receptor (ER), the progesterone receptor (PR), or both.² About 50 to 60% of patients with hormone receptor-positive tumors respond to hormonal therapy. Approximately 20 to 35% of patients with hormone receptor-positive metastatic breast cancer will experience an objective response to initial hormone therapy. However, a portion of hormone receptor-positive patients will not respond.

Data are evolving in preclinical models demonstrating that estrogen modulates angiogenesis, in part through effects on VEGF.³⁻⁶ Data also suggest that estrogen (E₂) modulates VEGF-induced angiogenesis in physiologic and pathologic conditions. One study in an androgen-dependent male mouse model of breast cancer demonstrated that castration resulting in the removal of androgen causes tumor regression. There was also a reduction in tumor vasculature in response to castration and androgen deprivation that correlated with a decrease in VEGF at the molecular level, particularly 7 days after castration.⁷

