Thus, it is also a highly selective inhibitor of aromatase. The high potency and selectivity of letrozole explains its favorable pharmacological profile and high therapeutic index. In postmenopausal patients with advanced breast cancer, daily doses of 0.1 to 5 mg letrozole suppressed plasma levels of estradiol, estrone and estrone sulfate by 75-95% from baseline.¹⁴

- 2.1.2.2 Clinical Information: A Phase III global, multicenter, randomized clinical trial evaluated letrozole (2.5 mg/day) as a first-line hormonal therapy as compared to the present standard of treatment tamoxifen (20 mg/day).8 This trial accrued 907 postmenopausal women with ER and/or PR positive or unknown receptor breast cancer and locally advanced disease, metastatic disease, or loco-regional recurrence not amenable to treatment by surgery or radiotherapy. Patients received treatment until disease progression or discontinuation for any other reason. The primary endpoint was time to progression (TTP). Letrozole was superior to tamoxifen and reduced the risk of progression by 28% (hazard ratio 0.72, P < .0001). The median TTP was prolonged by 57%: 6.0 months for tamoxifen vs. 9.4 months for letrozole. The secondary endpoints included overall tumor response rate, clinical benefit, and time to treatment failure. Overall tumor response rate (complete and partial response) was significantly higher with letrozole (32% vs. 21%, P = .0002), irrespective of dominant site of disease. Clinical benefit (complete response, partial response or stabilization of disease) lasting at least 24 weeks was 50% for letrozole vs. 38% for tamoxifen (P = .0004). Time to treatment failure was significantly better for letrozole compared to tamoxifen (9.0 months vs. 5.7 months respectively, P = .0001.) The median overall survival was slightly prolonged for letrozole vs. tamoxifen (34 months vs. 30 months, respectively). This difference is not significant. However, the study design included a crossover to the other treatment arm at the discretion of the investigator. An analysis was done in the patients who did not crossover, which demonstrated a 15-month survival advantage in the letrozole treatment group. 15 The data cutoff for this analysis was September 2001 when median follow-up was 32 months with a maximum observation period of 57 months. Tolerability was similar in both arms of the trial, with 2% of patients on letrozole and 3% of patients on tamoxifen discontinuing therapy due to adverse events.

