5.1 Inclusion Criteria

A patient is eligible for enrollment if all of the following inclusion criteria are met.

- 5.1.1 Histologically confirmed invasive breast cancer
- 5.1.2 Stage IIIB, IIIC with T4 lesion or Stage IV disease
- 5.1.3 ER-positive and/or PR-positive of primary or secondary tumor tissue
- 5.1.4 Women age \geq 18 years
- 5.1.5 Postmenopausal status defined by one of the following criteria:
 - Age 56 or older and history of at least 12 months without spontaneous menstrual bleeding prior to study entry, or
 - Age 55 or younger with a history of at least 12 months without menstrual bleeding, whether spontaneous or from a prior hysterectomy, with a documented estradiol level within the institutional/laboratory postmenopausal range, or
 - Prior documented bilateral oophorectomy or
 - Ovarian suppression by a luteinizing hormone-releasing hormone (LHRH) agonist. Medical ovarian suppression can be initiated any time prior to or at the start of protocol therapy, and continued throughout the duration of the trial.
- 5.1.6 Patients must have an ECOG performance status 0, 1, or 2 (Appendix A).
- 5.1.7 Patients must have normal organ and marrow function as defined below:
 - ANC count $\geq 1200/\mu L$
 - Platelets $\geq 100,000 / \mu L$
 - Total bilirubin ≤ 1.5 X institutional ULN
 - AST(SGOT)/ALT(SGPT) ≤ 2.5 X institutional ULN, (≤ 5 X ULN if liver metastases present)
 - Creatinine ≤ 1.5 X institutional ULN
- 5.1.8 Patients can have non-measurable disease or measurable disease according to RECIST (Section 9).
- 5.1.10 Life expectancy of 3 months or longer

Phase I/II Trial of Letrozole and as First-Line Therapy in Postmenopausal Women with Hormone Recentor Positive Locally Advanced or Metastatic Breast Cancer PI: I

- 5.1.11 Able to swallow and retain oral medication
- 5.1.12 Written informed consent

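### Section 16.2 attributes the 50% null to receptor-positive patients, but the source trial also took receptor-unknown women, so the stated 4.3% is not shown to guard against a letrozole-like result in the women enrolled

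*Combined protocol and SAP*

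**What the plan says.** Section 16.2 states that "single-agent letrozole in the first-line treatment of patients with hormone receptor-positive metastatic breast cancer had a clinical benefit rate of 50"% compared to tamoxifen, and builds the test on that figure: "the null hypothesis is that the clinical benefit rate of the combination therapy is less than or equal to 50"%, while "the alternative hypothesis is that the clinical benefit rate of 67% or more is of considerable interest". The decision rule is that "the combination therapy will be accepted if there are at least 35 responders out of 58 patients". The section gives a type I error of 4.3% and a power of 82.7%.

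Section 2.1.2.2 describes the letrozole-versus-tamoxifen trial in which "Clinical benefit (complete response, partial response or stabilization of disease) lasting at least 24 weeks was 50% for letrozole vs. 38% for tamoxifen". Its population was wider than 16.2 says: "This trial accrued 907 postmenopausal women with ER and/or PR positive or unknown receptor breast cancer". The 50% is given for the letrozole arm as a whole. The document gives neither the share of women with unknown status nor the benefit rate by receptor status.

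Inclusion criterion 5.1.3 of the present trial requires "ER-positive and/or PR-positive of primary or secondary tumor tissue".

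**The concern.** The phase II part has a single arm, so the historical 50% is its only comparator. Section 16.2 presents that figure as coming from women like those to be enrolled, and section 2.1.2.2 shows that it did not come only from such women. A receptor-unknown group plausibly contains some receptor-negative women, since section 2.1 puts about 75% of breast cancers as receptor-positive. Section 2.1.1 explains that aromatase inhibitors act by depriving the tumor of estrogen, so receptor-negative women should benefit less. Taken alone, removing them would raise the letrozole rate above 50%.

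At stake is what the 4.3% protects against. If letrozole alone does better than 50% in receptor-positive women, a combination that adds nothing passes the rule more often than the plan suggests. The plan neither mentions the difference in population nor justifies carrying 50% across.

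**Working it through.** **Inputs from the document.** n = 58, null 50%, target 67%, go at 35 or more (all 16.2); about 75% of breast cancers receptor-positive (2.1).

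**Step 1: reproduce the stated figures.** For a go at r or more, the exact tail is P(X ≥ r) = Σ C(58,k) p^k (1−p)^(58−k), summed over k = r to 58.

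- r = 35, as printed: 7.40% at p = 0.50; 88.71% at p = 0.67.
- r = 36: 4.35% at p = 0.50; 82.65% at p = 0.67.

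The stated 4.3% and 82.7% therefore belong to at least 36 of 58, to within 0.1 percentage point. The printed rule of at least 35 does not give them.

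**Step 2: false-go probability by letrozole rate.** Assume sorafenib adds nothing, so that p is the letrozole rate in the enrolled women.

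| Letrozole rate | Cut-off 36 | Cut-off 35 |
|---|---|---|
| 50% | 4.3% | 7.4% |
| 51% | 5.9% | 9.8% |
| 52% | 8.0% | 12.7% |
| 52.5% | 9.2% | 14.3% |
| 53% | 10.5% | 16.1% |
| 55% | 17.1% | 24.7% |

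One percentage point is enough to take cut-off 36 past the plan's own 5% limit.

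**Step 3: how far the rate might move.** Let u be the share of source patients with unknown status, x the benefit rate in receptor-positive women and q the rate in true negatives. Assume that 75% of the unknowns are truly positive, borrowing the general figure from 2.1. The whole-arm rate then satisfies

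0.50 = (1−u)x + u(0.75x + 0.25q), so x = (0.50 − 0.25uq)/(1 − 0.25u).

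The values of u and q are assumptions; the document gives neither.

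| u | q | x | Cut-off 36 | Cut-off 35 |
|---|---|---|---|---|
| 10% | 20% | 0.495/0.975 = 50.8% | 5.5% | 9.2% |
| 20% | 20% | 0.490/0.950 = 51.6% | 7.1% | 11.4% |
| 20% | 0% | 0.500/0.950 = 52.6% | 9.5% | 14.8% |
| 30% | 20% | 0.485/0.925 = 52.4% | 9.0% | 14.1% |
| 30% | 0% | 0.500/0.925 = 54.1% | 13.7% | 20.4% |
| 40% | 0% | 0.500/0.900 = 55.6% | 19.4% | 27.5% |

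If receptor-unknown women did as well as receptor-positive ones, x stays at 50% and nothing changes.

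**The case against.** The strongest reply is that type I error is conditional on the stated null. Section 16.2 defines that null as 50% or less, and at 50% the 4.3% is right for a cut-off of 36. A different letrozole rate changes how useful the null is, not its alpha. This stands. A reader might infer that the population mismatch makes the stated error rate wrong, and it does not. What is wrong at 50% is the pairing of 4.3% with a cut-off of 35, which is a separate defect.

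Nor is the net direction established. Prior adjuvant tamoxifen or aromatase inhibitor is allowed (5.2.1), which may lower the letrozole-alone rate. Stable disease must last 6 months here against 24 weeks in the source, which is slightly stricter. In the other direction, restricting phase II to patients with at least two cycles (16.2) tends to raise the observed rate. Sampling error is also of similar size: assuming about 453 letrozole patients (half of 907), the 95% interval is 0.50 ± 1.96 × √(0.25/453), or 45.4% to 54.6%.

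A reader might take the statement in 2.1 that "About 50 to 60% of patients with hormone receptor-positive tumors respond to hormonal therapy" as evidence that the null is too low. It concerns hormonal therapy in general, leaves response undefined, and includes 50% in its range.

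Finally, the go rule only selects the combination for further study, and section 17.5 says superiority to letrozole alone is unclear. That limits the harm. It does not excuse misdescribing the sole comparator.

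**Conclusion.** The point holds in a limited form. Section 16.2 misdescribes the population behind its null, and the plan gives no reason why 50% should apply to receptor-positive women. The stated 4.3% is therefore not shown to protect against a letrozole-like result in the enrolled population.

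Under the assumptions in the working, the receptor-positive letrozole rate is 50.8–55.6%. The false-go probability is then 5.5–19.4% at cut-off 36 or 9.2–27.5% at cut-off 35. These ranges illustrate the one factor considered alone and are not estimates. The documents do not support saying that the null is too low on balance, because offsetting differences exist and none can be quantified from the text.

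It would also be tempting to conclude that the null should be raised to 55%. The documents contain no receptor-positive rate to justify that. With 58 patients it would need 39 or more (alpha 3.9%, power 54.6% at 67%), a trade-off the evidence does not require.

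**What to change.** Make four changes in section 16.2:

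1. Say that the 50% comes from women with receptor-positive or receptor-unknown disease.
2. Reconcile the cut-off with the error rates: at least 35 of 58 goes with alpha 7.4% and power 88.7%; at least 36 goes with the stated 4.3% and 82.7%.
3. Replace the single 4.3% with a short table of false-go probabilities at letrozole rates of about 50 to 55%, using the adopted cut-off. The 50%, 52.5% and 55% rows of the Step 2 table would do.
4. State that a go means exceeding a historical 50% from a mixed population, and report the observed rate with its exact confidence interval.

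The cost is a few sentences and a table, and a less favourable stated false-positive rate. The null and the sample size stay as they are.
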